### List of contraindicated drugs

As documented in Rossi et al. (2009), taking one the following drugs may lower seizure thresholds. Note, however, that this is not an exhaustive list. Moreover, it is a list that may be out of date. Thus, any medication being taken by a participant will be cross-referenced against an updated list maintained on <https://www.epilepsy.com/learn/professionals/resource-library/tables/drugs-may-lower-seizure-threshold> AND reviewed by a TMS trained physician [REDACTED] to determine its potential to alter risk for seizure with TMS.

This list of drugs is current as of the time of the writing of the protocol. It is only stated that it may be out of date because new drugs are constantly developed and for that reason we will rely primarily on the judgement of the medical doctor and not on this list.

Imipramine  
 Amitriptyline  
 Doxepine  
 Nortriptyline  
 Maprotiline  
 Chlorpromazine  
 Clozapine  
 Foscarnet  
 Ganciclovir  
 Ritonavir  
 Amphetamines  
 Cocaine  
 MDMA (ecstasy)  
 phencyclidine (PCP, angel's dust)  
 ketamine  
 gamma-hydroxybutyrate (GHB)

v. 01/21/2019

alcohol  
theophylline  
mianserin  
fluoxetine  
fluvoxamine  
paroxetine  
sertraline  
citalopram  
reboxetine  
venlafaxine  
duloxetine  
bupropion  
mirtazapine  
fluphenazine  
pimozide  
haloperidol  
olanzapine  
quetiapine  
aripiprazole  
ziprasidone  
risperidone  
chloroquine  
mefloquine  
imipenem  
penicillin  
ampicillin  
cephalosporins  
metronidazole  
isoniazid  
levofloxacin  
cyclosporine  
chlorambucil  
vincristine  
methotrexate  
cytosine arabinoside  
BCNU  
Lithium  
Anticholinergics  
Antihistamines  
Sympathomimetic

## 5. Recruitment Methods

Recruitment will be initiated in response to an e-mail contact from the participant regarding an advertisement. Advertisements may be posted as flyers, placed on tables, in community newspapers, e-mail digests, and on-line. See attached recruitment document. We will not initiate contact with students, but will wait for them to approach us for information about the studies.

The researcher conducting the recruitment and screening will be knowledgeable about the methods used (behavior, MRI, EEG, and TMS) and will be able to answer any specific questions that the participant may have regarding the risks or procedures associated with the methodology. Safety screening will closely follow published safety guidelines for TMS (detailed in Rotenberg et al., 2014), MRI and EEG. During each experimental session, the researcher will remind the participant that this study is for research purposes only, and not intended to be a clinical intervention or treatment in any way. The researcher will also remind the participant that all study results will be analyzed at the group level, and that individualized study results other than a copy of the participant's structural MRI will not be available.

v. 01/21/2019

Participants will be pre-screened by phone or in-person interview for neurological, psychiatric, or medical contraindications, which may prevent them from participating in the TMS or MRI portions of this experiment. Either [REDACTED] will carry out the pre-screening process using the [name] Initial Contact & Screening Form (see attached). During pre-screening, the researcher will also describe the experimental methods utilized in this study so that the potential participant can make an initial informed decision about their interest in participating. Women will specifically be asked to indicate if there is any likelihood of pregnancy; this will be an additional exclusion criterion since the risks of TMS and MRI to the fetus are unknown. Additionally, we will screen participants for medications that increase risk from TMS. The researcher will discuss any questionable potential exclusionary criteria with one of our collaborating Psychiatrists, [REDACTED] before scheduling the experimental research session.

On the day of the MRI, participants will also be required to fill out the Magnetic Resonance Facility (MRF) Procedure Screening Form (see attached), which will be reviewed by the researcher and MRI technician, as required by Brown University.

On the day of a EEG and/or EEG-TMS session, participants will receive a second follow-up screening questionnaire to fill out (see [name] Patient Information & Secondary Screening Form). This questionnaire is intended to “double-check” for any TMS-exclusionary criteria, particularly any medications or other medical conditions that have changed in the time since the initial phone screening and experimental session, and also to collect valuable demographic and other information pertinent to study design and interpretation. [REDACTED] will review the screening questionnaire before the study session begins.

After taking part in one of our experimental sessions, participants can indicate whether or not they wish to be re-contacted by our lab to take part in additional sessions.

## 6. Compensation / Reimbursement

Participants will be paid in cash at the end of an experimental session, with a total amount per study visit as follows:

- I. MRI session ~ 1.5 hours, \$25 total
- II. EEG session without TMS ~2.5 hours, \$40 total
- III. EEG session with TMS (somatosensory cortex) ~3.5 hours, \$60 total
- IV. EEG TMS with TMS (control region) ~3.5 hours, \$60 total

Participants will be scheduled for the time allotted above, but if the session runs over we will pay them an additional \$15/hour. This overtime is not expected to occur often, and highly unlikely to exceed one hour in total. We do not anticipate that there will be any additional costs to the participant, as we will be recruiting from the local Providence, RI area.

If a participant decides to stop the study or withdraw for any reason before completing the study procedure during a study session, they will still be compensated \$15/hour for their time, rounded up to the nearest hour. For example, if we begin consenting a participant and realize within an hour of arrival that they cannot or will not participate in the study, they will be paid \$15 total for their time.

If the investigator decides to discontinue, the participant will be told the reason why and how they will be compensated. The researcher will offer to further explain or answer any additional questions the participant asks.

**7. Potential Research Risks / Discomforts to Participants.** *In order to approve the research, the IRB must consider the risks posed to participants by the research and any efforts to mitigate those risks. The IRB needs to determine that the risks have been both minimized and are reasonable in relation to the anticipated benefits to participants, as well as to the importance of the knowledge that may be gained. The IRB will also consider whether the informed consent process provides potential participants with an accurate and fair description of the risks or discomforts.*

All members of the research staff will undergo training in appropriate usage, safety, application, and maintenance of research equipment. This includes tactile stimulation, TMS, and EEG. [REDACTED] completed technical and safety training at [REDACTED].

[REDACTED]. She also has extensive experience carrying out MRI studies prior to attending Brown University, and will take part in MRI safety training at the Brown University MRF prior to scheduling any participants for an MRI session of the study. [REDACTED] will be present at all study sessions, along with at least one additional researcher. [REDACTED] have also both received extensive training in the responsible conduct of research, including training from Brown University and CITI training.

There is no deception in these experiments. But, to prevent introducing bias into the results, participants will not be informed of the specific hypotheses or experimental conditions until after the experiment is complete, at which point participants will be fully debriefed. We do not anticipate any physical, psychological, social, legal, or other risks from participation in the cognitive tasks themselves, apart from the potential for boredom and/or mild fatigue.

The potential for loss of electronic and paper records of personal information used for screening may place the participant at low risk for loss of privacy. To reduce the risk of loss of private information, participant identifiable information will be stored separately from individual data and any screening conversations will take place in private. All electronic records will be maintained on password protected file servers in a locked office, further protected by firewalls and other security procedures. Paper records will be maintained in locked file cabinets in locked offices.

## MRI

There are no known significant risks associated with participation in MRI at the levels of magnetic field proposed here, beyond those due to the effect of a magnetic field on an implanted metal fragment or medical device. Hence, all participants are extensively screened for implanted metal. Persons at primary or secondary risk based on an implanted object or medical device will be excluded according to MRF operating procedures. Moreover, no personnel are permitted in the scanner room with any metal on their person. As such, we do not anticipate any significant risk from the application of these procedures. In rare cases, a participant will become anxious because of lying in an enclosed space. We will exclude participants who report a history of anxiety in enclosed spaces, and we will terminate the session of a participant who expresses anxiety about lying in the bore.

All participants will be able to stop the session at any time by squeezing a ball held in one hand. The ball activates a buzzer in the control room. There is also an intercom voice link with the control room that allows verbal communication between participant and experimenters.

## Tactile Stimulation

The design of this stimulator has been used in multiple prior studies without causing injury to the skin ([name] et al.; Sliva et al., 2018). In past experiments, the sensation has been well tolerated and participants have reported that it is not uncomfortable.

Piezoelectric devices can only provide small forces, so even if the device were to malfunction, tissue damage is highly unlikely. The design of the stimulator also inherently limits the amount of pressure that can be applied. Reasonable safe ranges for maximum pressure applied to the skin are known and will be followed conservatively. Additionally, participants will be monitored continuously by a member of the trained research staff while the stimulator is operating, so that the experiment can be aborted if the participant experiences any discomfort or a device malfunction.

Although constant exposure from the device for long periods of time (upwards of 2+ hours) may cause tenderness or a slight scratching to the area of contact, we anticipate participants being exposed for no longer than 1 hour per session. Furthermore, the participant is free to stop the testing at any time if any discomfort.

## EEG

EEG is a safe and painless technique that is routinely used in clinical medicine. The amount of electricity is minimal and there is no risk of electric shock or discharge. The electrode, the cables, and the computer will be tested by biomedical engineers who will certify their safety. Though it is commonly regarded to be a safe technique, there is a possibility participants may experience side effects or discomfort:

(1) EEG may cause minor skin irritation from the use of electrodes, a mild electrolyte gel, and/or adhesive disc electrodes applied to the mastoid bone behind the ear or on the nose. Scraping of the scalp may occur when applying conductive electrode gel scraping of the scalp, which might also add to any discomfort or redness.

(2) Participants may also experience discomfort as a result of sitting still and minimizing self-adjustments during study sessions.

(3) They may also experience discomfort from having the aforementioned electrolyte gel in their hair; however, it is water-soluble and easily rinsed out of one's hair.

During usage of EEG equipment, a member of the trained research staff will continually monitor participants to ensure safety. Furthermore, prior to each trial the electrode cap will be thoroughly cleaned and disinfected to eliminate any transfer of biological debris or contaminants from previous participants. Participants are free to stop the experiment at any time if they no longer desire to continue.

The EEG device will be battery-powered or otherwise electrically isolated from building current.

## TMS

We note that as this protocol covers basic research and does not confer a direct benefit for participants in the experimental condition, standard random assignment is appropriate for any between-participant design. Following participation, we will fully debrief participants about the use of control stimulation.

TMS is low risk given that the stimulation parameters being used are within established safety norms), and we will only enroll healthy participants without contraindication for TMS. In what follows, we detail the specific risks associated with this protocol and the steps we will take to protect against risk beyond those already described in relation to the consent process:

(1) Heating, induced voltages, and magnetic field effects: The action of the magnetic field on any implanted or worn metal in, on, or around the head poses a significant risk. Magnetic fields can move or dislodge metal, induce current in conductive metals, cause heating around metal components, and/or affect the operation of any metal device. Thus, it is crucial to screen participants for any irremovable metal in or around the head.

(2) Hearing changes: Movement of the TMS coil within its casing when current is passed through it produces an audible "click". Though this click is often not perceived as loud due to the stapedial reflex, it can nevertheless reach 140 dB or more of sound pressure. This exceeds OSHA sound level limits and could produce changes in hearing levels if exposed repeatedly. Thus, we will require all participants to wear earplugs.

(3) Induced seizure: Though exceedingly rare even in patients with epilepsy, induction of a "generalized" seizure is the most severe adverse event associated with TMS. A seizure is an episode of excessive brain activity and stiff muscle activity (often referred to as a "convulsion" or "fit"). Seizure risk increases at high stimulator output intensities, at high frequencies of stimulation, with multiple repeated trains of stimulation, with long durations of stimulation, with short inter-train-intervals, and when stimulating participants with reduced seizure thresholds. However, the risk of seizure induction is minimal to negligible if TMS parameters are kept within the prescribed consensus safety parameters (Rossi et al., 2009), and participants are carefully screened for seizure risk. All the TMS protocols proposed here are will be within prescribed safety limits, and a health screening form will include questions to identify participants with potential seizure risk.

(4) TMS application site (scalp) discomfort/headache. The stimulation itself is felt as a tapping sensation on the scalp. The tapping induced by rTMS at high stimulator output intensity can feel sharper and even painful. In addition to a tapping or percussion sensation on the head, muscles and peripheral nerves in the head and face react to TMS with sensations such as twitching of superficial muscle groups.

As described above, acute, severe adverse events during the course of the TMS experiment could include things like superficial burns of participant's skin from TMS coil heating or induction of a generalized "seizure". Other adverse events such as fainting, severe headache, nonspecific stress reaction are possible with TMS and also with other types of brain research. Though our protocol and procedures minimize the risk of these adverse events occurring, all research personnel will be trained to observe the signs of an adverse event, terminate study procedures, and call Brown's Emergency Response System, if it appears a participant is experiencing an adverse event.

## Procedures in the case of an adverse event

As described above, acute, severe adverse events during the course of the TMS experiment could include things like superficial burns of participant's skin from heating of the TMS coil or EEG electrodes, or induction of a generalized "seizure". Other adverse events such as fainting, severe headache, and nonspecific stress reaction are also possible with TMS and other types of brain research.

Though our protocol and procedures minimize the risk of these adverse events occurring, all research personnel will be trained to observe the signs of an adverse event and take the appropriate steps to alleviate any distress a participant may be feeling. For example, the researcher will terminate study procedures and call Brown's Emergency Response System (Brown EMS) if it appears that a participant is experiencing a severe adverse event such as a seizure. The Brown University EMS is a blended volunteer/paid service licensed by the State of RI to provide all levels of pre-hospital care to the Brown community. They provide Basic and Advanced Life Support (BLS and ALS) care and transport 24 hours a day year round except during brief interruptions for periodic maintenance. Brown EMS is staffed by a corps of student volunteers who are licensed RI EMTs and who are assisted by a staff of student and non-student ALS Providers who oversee care when needed.

Research personnel will also be trained to "check in" with study participants throughout study sessions, so that participants feel comfortable communicating any distress they may be feeling to the researcher. Researchers will additionally specifically ask participants about their well-being after the study session is over, and inquire if any of the aspects of the experiment (e.g. sound of TMS clicks) negatively impacted them in any way.

Any adverse event that comes to the researcher's attention either by observation or communication with the participant will be documented and communicated to the IRB.

Two researchers will always be present at any given TMS session in case of an emergency so that one researcher can stay with the participant, while the other researcher seeks help from Brown EMS and the study Principal Investigator.

### **Safety plan for seizures**

The following plan has been adapted from the Center for Disease Control, ([http://www.cdc.gov/epilepsy/basics/first\\_aid.htm](http://www.cdc.gov/epilepsy/basics/first_aid.htm))

1. Keep calm and reassure other people who may be nearby.
2. Immediately end on-going experiment, remove any equipment involved (tACS, tactile stimulator, EEG), and remove any other hard or sharp materials in the area near the participant.
3. Call Brown EMS at [contact].
4. Make note of when seizure begins.
5. Recline participant in testing chair, if at all possible, making sure arm rests are in place so the participant does not fall out of the chair.
6. If possible, turn the participant gently on their side.
7. Remove eyeglasses and loosen ties or anything around the neck that may make breathing difficult.
8. Stay with the participant until EMS arrives.
9. Be friendly and reassuring as consciousness returns.
10. Contact the Principal Investigator as soon as possible.

### **DO NOT ATTEMPT THE FOLLOWING:**

- 1) **Do not** put anything in the person's mouth. Do not attempt to hold or touch the patient's tongue, face, or head during a seizure.
- 2) **Do not** hold the person down or try to stop his movements.
- 3) **Do not** attempt artificial respiration.
- 4) **Do not** offer the person water or food until fully alert.
- 5) **Do not** administer any medications to the person.
- 6) **Do not** permit the person to leave the research area or go home without evaluation by a medical professional.

The safety plan detailed above will be posted in the TMS suite, both in the testing room and in the outer control room (see attached Safety Plan Poster). In addition, the telephone number for Brown EMS ([name]) will be posted clearly above the telephones available in the TMS suite.

**8. Potential Benefits of the Research. NOTE: Compensation for participation is not a benefit and should not be included in this section.** *In order to approve this research, the IRB must determine that the potential benefits to research participants are reasonable in relation to the potential risks. Very often, research at Brown does not include potential direct benefits to participants, but may only benefit society as a whole by helping researchers.*

The proposed research does not guarantee direct benefits to the participants beyond the opportunity to participate in a scientific enterprise. There is a potential indirect benefit of this research as it may advance understanding of human sensory processing, and the effects of TMS on the human brain. TMS is currently FDA approved for treatment-resistant depression, and is being actively investigated for a wide range of other disorders, including several that affect touch processing (e.g. chronic pain and autism). In this way, this study may ultimately contribute to disease etiology and treatment.

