##### EEG

During the tactile detection task, participants will receive continuous non-invasive monitoring and recording of changing brain electrical potentials via scalp EEG. This will allow us to link perception to neural dynamics. To do so, we will use two 32-channel Brain Vision amplifiers, for a total of 64 channels. We will use either actiCHamp Plus or BrainAmp series amplifiers, with either passive BrainCap TMS or active actiCAP slim/snap electrodes and mesh caps. All of this equipment is specifically designed and marketed (vendor Brain Products) to be safe and compatible with concurrent TMS application.

In order to carry out EEG, we will place the mesh electrode caps on the participant's head. We will then prepare the skin underneath each electrode in order to get a good electrical signal. To do so, we may first clean the skin underneath each electrode with an alcohol swab, as needed. This step is used mainly if the participant's hair is unwashed, or if we are using a passive electrode cap. We will then very gently abrade/exfoliate the skin using either a blunt-tipped needle (active electrode caps), or a cotton-tipped wooden swab and exfoliating gel (passive electrode caps), while applying a small amount of adhesive gel into each metal ring. This process is not painful, and may feel like a light scratching sensation. The gel is similar to the consistency of hair gel and can be washed out with water. We have a single-occupancy bathroom down the hall from our EEG & EEG-TMS testing rooms in which there is a sink and shower for participants to wash their hair after the experiment. We will also provide participants with clean towels and shampoo.

We will request that participants try to stay as still as possible while we are actively recording EEG data to prevent degradation of the signal. We will communicate to the participant when we are in a phase of the experiment when this is necessary, and when they can relax and move in an unrestricted manner.

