### Neuronavigation

When the neuronavigation system is used, the participant will wear a headband or plastic eyeglasses with an attached position tracker. An additional head-tracking tool will identify the location of specific fiducial landmarks on the head as recorded by an optical position sensor (i.e., a special camera with two lenses) mounted to the wall. The coil position is then tracked relative to a canonical brain, the participant's own anatomical MRI, and/or an overlaid fMRI image, and can be visualized by the neuronavigation computer throughout the stimulation session. In cases where the participant's own brain image is used for localization, an anatomical MRI will have been collected during a prior MRI session. We will inform participants that we must use their neuroimaging data from this previous experiment during the TMS consent process, and will obtain their consent to do so.

Stimulation is triggered either manually by the experimenter or automatically by the experimental script. There is no difference in risk or the functioning of the stimulator with either of these options. When the strong current passes through the coil, there is a small degree of movement of the wire coil within its protective casing. This produces an audible "click" when the coil is pulsed. Participants will be required to wear ear plugs to protect them from exposure to this noise.

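### The seizure plan tells staff to remove EEG equipment at once but forbids touching the head during a seizure, and does not say how the EEG cap is to be handled

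*Protocol*

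**What the plan says.** The plan stands in section 7 of the protocol, under Safety plan for seizures, and is followed by a list of prohibited actions.

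- Step 2: "Immediately end on-going experiment, remove any equipment involved (tACS, tactile stimulator, EEG". The bracketed list ends there. The sentence goes on to other hard or sharp objects near the participant.
- Step 7: "Remove eyeglasses and loosen ties or anything around the neck that may make breathing difficult".
- Step 9: "Be friendly and reassuring as consciousness returns".
- First prohibition: "Do not attempt to hold or touch the patient's tongue, face, or head during a seizure".
- After the prohibitions: "The safety plan detailed above will be posted in the TMS suite, both in the testing room and in the outer control room".

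Two parts of section 3 show what is worn on the head. In the EEG section, "we will place the mesh electrode caps on the participant's head", and gel is then worked in under each electrode of a 64-channel system. In the Neuronavigation section, when navigation is used, "the participant will wear a headband or plastic eyeglasses with an attached position tracker".

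**The concern.** The seizure plan is described as adapted from a general first-aid source. Such a source has no need to deal with a participant who wears recording equipment on the head. Here the participant wears an electrode cap in every TMS-EEG session, and nothing in the plan adjusts the ban on touching the head to allow for it.

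Section 7 ranks an induced generalized seizure as the gravest adverse event of TMS, and this plan is the text to be displayed for that event. A researcher who follows step 2 to the letter and takes the cap off would breach the first prohibition. One who follows the prohibition to the letter would leave step 2 undone. The matter does not touch endpoints, sample size or inference. It concerns whether a written safety procedure can be carried out as written.

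**Working it through.** There is no figure to reproduce. The check sets the instructions beside each other.

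| Item in the plan | Stated timing | Qualifier or exception | Where the object is | Contact with head or face |
|---|---|---|---|---|
| Step 2, EEG equipment | At once | None | Cap on the head (EEG section) | Needed to take the cap off; not needed if only disconnection is meant |
| Step 7, eyeglasses | None | None | Face; may be the navigation tracker | Possibly little, if lifted by the frame |
| First prohibition | During a seizure | None | Tongue, face, head | Forbidden |

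**Does step 2 fall within the seizure?** Yes, on its own wording. It opens with an adverb of immediacy and comes before the call to EMS (step 3), the arrival of EMS (step 8) and the return of consciousness (step 9). The numbering is not strictly chronological, since noting when the seizure began is step 4. The conclusion does not need the numbering, because step 2 states its own timing.

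**Does step 2 reach the cap?** This is an inference, though the natural one. The text names EEG and not a cap. The verb is remove, its object is any equipment involved, and the EEG item on the participant is the cap. A gelled cap fitted over the head cannot realistically be taken off without touching the head.

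**Is there a softener?** Steps 5 and 6 are hedged to what is possible. Step 2 is not.

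**Could the prohibition mean restraint only?** That is unlikely. Holding the person down has its own entry as the second prohibition, and the first one covers touching as well as holding.

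**Does step 7 conflict in the same way?** Less clearly. It precedes step 9 in the list but gives no time of its own, and the prohibition applies only while the seizure lasts. Step 7 could be carried out once the seizure has stopped, or with little contact. If the tracker is worn, it would also come under step 2's general wording, although it is not named there.

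**Reach of the plan.** Section 4 plans 25 participants for EEG with TMS, each with sessions III and IV: 25 x 2 = 50 sessions. Section 3 says that participants are not required to return for later sessions, so 50 is a ceiling on planned sessions. It is not a count of seizures or of conflicts.

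**The case against.** The best reply is that step 2 is about clearing hazards. Its sentence runs on to other hard or sharp materials nearby, which groups the equipment with objects around the participant, and EEG equipment includes amplifiers as well as the cap. On that reading staff would disconnect the EEG and move it away, and the head need not be touched. This reading is open and it stands as a possibility. But the plan does not state it, and staff would have to supply it themselves during an emergency. If disconnection is what is meant, the wording still has to say so.

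Several stronger claims are tempting, and the protocol does not support them:

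- A reader might infer that the plan expressly orders the cap off, so that both rules can never be obeyed. The cap is inferred from the EEG section, and the impossibility holds only on the natural reading of step 2.
- A reader might count step 7 as a second full contradiction. Its lack of timing and the small contact needed make it secondary.
- A reader might say that the poster is the only guidance staff will have. Under Procedures in the case of an adverse event, all research personnel are to be trained to recognise such events and respond. The protocol does not say which of the two rules the training will teach, but posting is not the sole safeguard. The attached poster is also not among the documents at hand, so its exact wording cannot be checked.
- A reader might fear that removing the cap delays the EMS call. The same section requires two researchers at each TMS session, one to stay with the participant and one to seek help, so the call can run in parallel.

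**Conclusion.** The point holds in limited form. Read naturally, step 2 and the first prohibition give conflicting instructions for the EEG cap, and nothing in the plan resolves them. The eyeglasses in step 7, which may be the navigation tracker, add a weaker tension.

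This rests on two readings: that EEG in step 2 includes the cap, and that acting at once means acting during the seizure. The second follows from the step's own wording. The first is the natural sense but not the only one.

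The reach is at most 50 planned TMS-EEG sessions, and the conflict has effect only if a seizure occurs. Section 7 treats that as very rare, and as minimal to negligible in risk within the consensus stimulation limits and with screening. The case for acting is the gravity of the event and the small cost of the repair, not any expected number of occurrences. Which instruction is clinically right is outside this review.

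**What to change.** Reconcile the numbered steps and the list of prohibitions before the plan is posted. The study's TMS-trained physician, a role the protocol already names under List of contraindicated drugs, should decide how and when each head-worn item (the EEG cap, and the tracker headband or eyeglasses) is handled in relation to the seizure. Step 2, step 7, the first prohibition and the Safety Plan Poster should then be reworded to agree, and staff training should use the same text. Step 2 should say outright whether removing the EEG means taking off the cap or disconnecting the equipment.

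Step 2 also lists tACS, which is not among the techniques this protocol describes, and does not name TMS. Correcting that list is a separate matter and would leave the present conflict in place.

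The cost is a few words in the protocol and on the poster, with an amendment submitted to the IRB. No staff, sessions or procedures are added.
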